#### **7.1.1.2 Other Medications Used During the 30 Days Prior to the Screening Visit (Visit -1) Washout Telephone Call**

The Washout Period should be initiated after clinical laboratory test results and 12-lead ECG results have been received and reviewed by the investigator. Eligible subjects will be contacted by a member of the site staff and provided with instructions on discontinuing any protocol-prohibited medications. During washout, a subject’s current prohibited medications (if applicable) will be discontinued for a period of a minimum of 5 times the half-life of the medication. Washout periods for prohibited medications are defined in [Table 2](#).

As part of the Washout Telephone Call, site personnel should perform the following procedures:

- Schedule the baseline visit (Visit 0)
- Review the inclusion/exclusion criteria
- Ask about any concomitant medications that the subject is taking. If new concomitant medications that require washout are noted, instructions for appropriate washout should be provided.
- Provide instructions on discontinuing any medication requiring washout.
- Determine if any AEs have occurred since the screening visit (Visit -1).

If a medication washout is not necessary, the Washout Telephone Call will include all the above procedures except providing instructions on discontinuing any current medications.

#### **7.1.1.3 Baseline Visit (Visit 0)**

Once the screening central clinical laboratory tests and 12-lead ECG results have been obtained, in addition to repeat assessments (if required), and the subject has completed the required washout period (if applicable), the subject will return to the site for the baseline visit (Visit 0).

Inclusion/exclusion criteria must also be reviewed during this visit to ensure subjects continue to meet all eligibility criteria.

Table 1 outlines all procedures to be conducted during the baseline visit (Visit 0) with further clarification provided below:

- For subjects with more than 30 days since the safety measurements at the screening visit (Visit -1) were collected, an abbreviated physical examination, clinical laboratory tests, and 12-lead ECG must be repeated, and the results reviewed by the investigator prior to the subject being enrolled.
- After 5 minutes rest, blood pressure, and pulse will be collected 3 times (with at least 2 minutes in between each collection) during the visit. The average of each set of 3 measurements will be used to determine continued participation in the study (see Section 4.4.1).
- Three ECGs will be taken, with approximately 5 minutes in between each one, to ensure appropriate baseline intervals are established. The investigator will perform the initial interpretation of the ECG immediately after collection to ensure the safety of each subject to continue with the study. The ECG tracing will be sent to the central reader for analysis. Upon review of the report from the central reader, the investigator will re-evaluate the clinical significance of the ECG in light of other safety data for the subject. If abnormal and significant results are observed following assessment by the central reader, the investigator, in consultation with the appointed CRO medical monitor, will confirm the subject's continued participation in this study.
- The C-SSRS "Since Last Visit" Version of the Pediatric/Cognitively Impaired Version should be completed.
- For eligible subjects, the investigator or assigned site staff designee will access the IWRS to enroll the subject and obtain an investigational product bottle number to dispense to the subject. Subjects will be dispensed a bottle of investigational product to cover them until their next regularly scheduled visit. Subjects will be instructed to take 1 capsule each day. Dosing will begin the morning following the baseline visit (Visit 0).

### **7.1.2 Double-blind Evaluation Periods**

#### **7.1.2.1 Fixed-dose Titration Period (Visits 1 to 3)**

During the first 3 weeks of treatment, visits will be scheduled every 7 days ( $\pm 3$  days) to assess safety, efficacy, and tolerability and to allow investigators to titrate subjects to their randomly assigned fixed-dose strength.

Subjects who are unable to tolerate investigational product should be discontinued from the study.

Throughout the Fixed-dose titration Period, subjects may attend the clinic for unscheduled visits to address any medical needs that arise between scheduled visits.

See [Table 1](#) for procedures that are completed at Visits 1 to 3. Further clarification for these visits is outlined below:

- At each visit during the Fixed-dose titration Period, subjects must return any empty or unused bottles to permit drug accountability and compliance to be assessed.
- Subjects will be dispensed a 10-count bottle of investigational product to cover them until their next regularly scheduled visit. Subjects will be instructed to take 1 capsule each day. Dosing will begin the morning following each visit.
- Blood pressure and pulse will be collected 3 times (with at least 2 minutes in between each collection) during the visit. The average of each set of 3 measurements will be used to determine continued participation in the study (see [Section 4.4.1](#)).
- Scales should be completed by the same rater with input from the same parent/LAR whenever possible.
- The C-SSRS “Since Last Visit” Version of the Pediatric/Cognitively Impaired Version should be completed during the Fixed-dose titration Period.

#### **7.1.2.2 Dose-maintenance Period (Visits 4 to 6)**

Following titration to the randomly assigned fixed-dose strength of SPD489/Placebo, subjects will continue daily morning treatment for an additional 3 weeks.

Throughout the Dose-maintenance Period, subjects may attend the clinic for unscheduled visits to address any medical needs that arise between scheduled visits.

[Table 1](#) outlines the procedures to be completed at each visit during the Dose-maintenance Period. Additional clarification on the procedures to be performed during the Dose-maintenance Period is provided below:

- Scales are to be completed by the same rater with input from the same parent/LAR whenever possible
- At each visit during the Dose-maintenance Period, subjects must return any empty or unused bottles to permit drug accountability and compliance to be assessed.
- Subjects will be dispensed a 10-count bottle of investigational product to cover them until their next regularly scheduled visit. Subjects will be instructed to take 1 capsule each day. Dosing will begin the morning following each visit.
- The C-SSRS “Since Last Visit” Version of the Pediatric/Cognitively Impaired Version should be completed during the Dose Maintenance Period.
- After 5 minutes rest, blood pressure and pulse will be collected 3 times (with at least 2 minutes in between each collection) during the visit. The average of each set of 3 measurements will be used to determine continued participation in the study (see [Section 4.4.1](#)).

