**Table 1 Schedule of Assessments**

Period	Screening and Washout			Dose-titration			Dose-maintenance			Safety Follow-up
	-1 (Screening)	Washout Telephone Call	0 (Baseline)	1	2	3	4	5	6/ ET	Telephone Call
Assessment Week	-4 to -1	-1	0	1	2	3	4	5	6	7
Assessment Day	-28 to -1		0	7	14	21	28	35	42	49
CGI-I k				✓	✓	✓	✓	✓	✓	
CSHQ k			✓	✓	✓	✓	✓	✓	✓	
Sleep diary l			✓	✓	✓	✓	✓	✓	✓	
C-SSRS k	✓		✓	✓	✓	✓	✓	✓	✓	
Suitability of subject to remain in study m			✓	✓	✓	✓	✓	✓		
Access IWRS	✓		✓	✓	✓	✓	✓	✓	✓	
Investigational product distributed			✓	✓	✓	✓	✓	✓		
Investigational product returned				✓	✓	✓	✓	✓	✓	
Investigational product compliance				✓	✓	✓	✓	✓	✓	
Concomitant medications	✓	✓	✓	✓	✓	✓	✓	✓	✓	✓
Adverse events	✓	✓	✓	✓	✓	✓	✓	✓	✓	✓

ADHD-RS-IV=ADHD Rating Scale-IV; BMI=body mass index; CGI-I=Clinical Global Impressions-Global Improvement; CGI-S=Clinical Global Impressions-Severity of Illness; CSHQ=Children's Sleep Habits Questionnaire; C-SSRS=Columbia-Suicide Severity Rating Scale; ECG=Electrocardiogram; ET=early termination; IWRS= Interactive Web Response System; K-SADS-PL=Kiddie-Schedule for Affective Disorders and Schizophrenia for School-age Children-Present and Lifetime Version-Diagnostic Interview

a Visit windows are ±3 days [in reference to the baseline visit (Visit 0) date] during the Fixed-dose titration and Dose-maintenance Periods. Safety Follow-up Telephone Call window is +3 days.

b Inclusion/exclusion criteria must be reviewed at the Washout Telephone Call and at the baseline visit (Visit 0).

c Medication history will include a lifetime history of pharmacologic and non-pharmacologic therapies for ADHD.

d An abbreviated physical examination, 12-lead ECG, and all clinical laboratory tests must be repeated and results reviewed by the investigator prior to the baseline visit (Visit 0) if more than 30 days have elapsed since the safety measurements at the screening visit (Visit -1) were collected. Results must be obtained and reviewed prior to determining eligibility.

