## 6.5 Subject Compliance

Subjects must be instructed to bring their unused investigational product and empty/used investigational product packaging to every visit. Drug accountability must be assessed at the container/packaging level for unused investigational product that is contained within the original tamper-evident sealed container (eg, bottles, trays, vials) or at the individual count level for opened containers/packaging. The pharmacist/delegated person will record details on the drug accountability form.

Subjects who have taken 80-100% of the investigational product are regarded as being compliant with the study protocol. Compliance must be assessed by the investigator.

The calculation of medication compliance is as follows:

$$\text{Compliance} = \frac{\text{Total Capsules Taken} \times 100}{\text{Capsules Prescribed by Protocol}}$$

When performing the calculation of medication compliance for investigational product, the total capsules taken must also include number of capsules not returned by the subject to the site.

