## 7 STUDY PROCEDURES

### 7.1 Study Schedule

The Schedule of Assessments (Table 1) details all procedures to be completed at each visit and should serve as the primary section of the protocol regarding visit-specific study procedures.

Clinician-completed rating scales and assessments conducted by the site ie, ADHD-RS-IV Preschool Version, CGI-I, and C-SSRS must be completed by the same rater whenever possible.

Throughout the Fixed-dose titration and Dose-maintenance Periods of the study, visits should be scheduled as outlined ( $\pm 3$  days) with reference to the Baseline visit (Visit 0). The Safety Follow-up Call should be scheduled 7 days post-last dose with a +3 day visit window.

Additional unscheduled visits and/or assessments may occur as needed for safety (eg, unscheduled visits for blood pressure and/or pulse measurements will be conducted as described in Section 4.4.1).

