8.2 Measurement of Treatment Compliance

Investigational product dosing compliance, during the Dose Optimization Period, the Dose Maintenance Period, and the whole Double-blind Evaluation Period, respectively, is defined as the total number of capsules taken by a subject during that period divided by the number of capsules expected to be taken during the same period multiplied by 100, that is (number of capsules actually taken \times 100 / number of capsules expected to be taken). The number of capsules taken is calculated by the number of capsules dispensed minus the number of capsules returned. If a bottle is not returned, the number of capsules returned for that bottle will be imputed to 0. The number of capsules expected to be taken is calculated as the number of days the subject is in the particular period multiplied by the number of capsules to be taken per day during that period. If the number of capsules taken or returned is missing, then the compliance will be missing.

For each study period, the compliance data will be reported using number of subjects, mean, SD, median, minimum, and maximum for the Safety Analysis Set by treatment group and pooled

doses. Furthermore, the compliance data will be categorized as <80%, 80-120%, or >120%, and it will be presented using subject counts and percentages for the Safety Analysis Set by treatment group and pooled doses.

Treatment compliance data will also be listed for all subjects in the Safety Analysis Set.

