10. EFFICACY ANALYSES

The primary and key secondary analyses, including their sensitivity analyses, will be based on the FAS and will be conducted on either the interim analysis dataset, which is defined in Section 2.6, or all cumulative data up to study completion, whenever it is appropriate. Specifically, these analyses will compare placebo and pooled SPD489 10, 20, 30 mg dose strengths together, excluding the 5 mg arm. For primary and key secondary endpoints, statistical tests are planned to control the study-wise type I error at the 2-sided 5% level, as described in Section 2.6. All other statistical tests will be 2-sided hypothesis tests performed at the 5% level of significance, with no adjustment for multiplicity. All confidence intervals (CIs) will be 2-sided 95% CIs, unless stated otherwise. Additionally, the dose response relationship evaluations will be performed over the DRAS and using appropriate datasets. For this analysis, all randomized investigational product groups, which include 0 (placebo), 5, 10, 20, 30 mg (SPD489) dose strengths will be used.

Baseline for all efficacy analyses is defined as the last valid value for the efficacy assessment prior to the first dose of investigational product. An efficacy measurement that is assessed more than 3 days after the date of the last dose of investigational product will not be included for analysis.

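### A 10-capsule bottle cannot cover the 13 days that the visit windows allow between visits, so a child can go undosed for 1 to 3 days up to and including the rating day

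*Protocol*

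**What the plan says.** **Supply.** Protocol 7.1.2.2 states: "Subjects will be dispensed a 10-count bottle of investigational product to cover them until their next regularly scheduled visit". Section 7.1.2.1 has the same rule for the titration visits, and 6.3.2 confirms the bottle size. The child takes one capsule a day and starts each new bottle the morning after the visit, so the visit-day dose comes from the old bottle. Leftovers do not carry over: 7.1.2.2 requires that "subjects must return any empty or unused bottles to permit drug accountability and compliance to be assessed", and 6.5 asks families to bring unused product to every visit.

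**Windows.** Table 1 footnote a sets ±3 days "in reference to the baseline visit (Visit 0) date", and Section 7.1 repeats that anchor for both treatment periods. For titration only, 7.1.2.1 also says "visits will be scheduled every 7 days" (±3 days), which could be read as visit to visit.

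**Safeguards.** On compliance, Protocol 6.5 says: "Subjects who have taken 80-100% of the investigational product are regarded as being compliant with the study protocol". SAP 8.2 works by study period: "the compliance data will be categorized as <80%, 80-120%, or >120" percent. SAP 10 drops only an efficacy measurement "assessed more than 3 days after the date of the last dose of investigational product will not be included for analysis".

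**The concern.** Ten capsules is 7 + 3. That covers the longest gap only when the earlier visit is fixed, as Visit 0 is, or when each window runs from the previous visit. Here both ends of every later gap can move, so the bottle does not do what the supply rule says it is for.

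A fully compliant family at a fully compliant site could therefore run out before the next visit. For the Visit 5–6 gap, the undosed days come immediately before the primary Week 6 rating of a once-daily drug. That would dilute the estimated effect, and neither the compliance bands nor the SAP's rule on time since last dose is designed to pick it up.

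**Working it through.** **Inputs.** Nominal visit days 0, 7, 14, 21, 28, 35, 42 (Protocol Table 1). Offset of each of Visits 1–6 from its nominal day: −3 to +3, counted from Visit 0 (Table 1 footnote a, 7.1). Ten capsules per visit, one a day, starting the next morning (7.1.2.1, 7.1.2.2).

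**Gap and shortfall.** With offset *a* at one visit and *b* at the next, gap = 7 + *b* − *a*. Doses needed = gap (the morning after one visit through the morning of the next). Shortfall = max(0, gap − 10).

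- Visit 0 to 1: Visit 0 is fixed, so the gap is at most 7 + 3 = 10 and nothing is missed. This reproduces the protocol's ten capsules.
- Each of the five later gaps: 1 to 13 days, with 7 × 7 = 49 offset pairs.

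| Days early + days late | Gap (days) | Doses missed | Pairs of 49 | Capsules/days |
|---|---|---|---|---|
| 4 | 11 | 1 | 3 | 10/11 = 90.9% |
| 5 | 12 | 2 | 2 | 10/12 = 83.3% |
| 6 | 13 | 3 | 1 | 10/13 = 76.9% |

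So 6 of 49 pairs run short. Of the 9 early-then-late pairs, the 3 that total 2 or 3 days miss nothing. These are counts, not probabilities.

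**Worst case at the primary rating.** Visit 5 on day 32 (35 − 3) and Visit 6 on day 45 (42 + 3) are both in window. Capsules cover days 33 to 42, and days 43, 44 and 45 are undosed. The rating is 45 − 42 = 3 days after the last dose. SAP 10 excludes only more than 3 days, so it stays in.

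**Would compliance flag it?** Judged visit by visit against 80%, only the 13-day gap is flagged. Over the maintenance period there are 7⁴ = 2,401 permitted offset patterns for Visits 3–6. With every available capsule taken, 846 contain at least one short gap and one falls below 80% (gaps 13, 1, 13: 21/27 = 77.8%). With Visits 3–6 on days 21, 28, 32 and 45, compliance is (7 + 4 + 10)/24 = 87.5%.

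**Effect on power.** The documents give no visit-timing data, so the timing patterns are assumptions, as is a loss of effect proportional to the undosed share of the gap.

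- Planned case: difference 8.4, SD 14, 90 versus 36 completers, nominal final level 0.0477, noncentral *t* with 124 df. The standard error is 14 × √(1/90 + 1/36) = 2.761, so the noncentrality is 8.4/2.761 = 3.04 and power is 85.0%, which matches the plan.
- Even use of the window: mean undosed share = (3 × 1/11 + 2 × 2/12 + 1 × 3/13)/49 = 1.71%; difference = 8.4 × (1 − 0.0171) = 8.257.
- Mostly on time (probabilities .03, .07, .15, .50, .15, .07, .03 for −3 to +3): mean undosed share 0.22%; difference 8.382.

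| Timing assumption | Visit 5–6 gaps short | Difference | Power |
|---|---|---|---|
| Mostly on time, independent offsets | 1.9% | 8.382 | 84.9% |
| Even use, independent offsets | 12.2% | 8.257 | 83.8% |
| Mostly on time, half keep the same offset | 1.0% | 8.391 | 85.0% |
| Even use, half keep the same offset | 6.1% | 8.328 | 84.4% |

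If a short gap instead removed the whole effect at that rating, which is an extreme assumption, power would be 83.7% (mostly on time) or 74.8% (even use), with independent offsets.

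**The case against.** The strongest case is that this hardly matters. With mostly punctual visits, power moves by about 0.1 percentage point, and nothing in the documents supports even use of the window. The rating scale scores how often symptoms occur over a period, and in a short gap the child was still dosed on 10 of 11, 12 or 13 days. The rule's stated purpose is to cover the child until the next visit, so a sensible site would book a covered date or seek more supply. Section 6.2.1 leaves supply to the interactive response system, whose manual may contain a resupply rule. The 7-day wording in 7.1.2.1 fits the bottle exactly. The SAP's 3-day limit may be a deliberate on-treatment margin. Capsule counts and visit dates would let any gap be reconstructed later.

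Most of this bears on size, and there it stands: the effect is probably small, the direction is conservative, and an unseen resupply rule cannot be excluded. It does not remove the conflict. The 7-day wording covers titration only, whereas Table 1, which 7.1 names as the primary source for visit procedures, and 7.1 itself anchor both periods on Visit 0. Coverage until the next visit is precisely what ten capsules fail to guarantee. Unscheduled visits are described for medical and safety needs, not for resupply. Being able to reconstruct a gap afterwards does not prevent the undosed rating.

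**Conclusion.** The concern holds as a minor design point. As written, the windows and the supply rule permit 1 to 3 undosed days ending on the rating day in 6 of 49 offset pairs for each of the five gaps after Visit 1, including the gap before the primary rating. Under the proportional-loss assumption the cost is between almost nothing and 1.2 percentage points of power (85.0% to 83.8%). None of these figures is a bound, and visits clustered at the window edges would cost more. Any bias is toward no difference, and type I error is not affected.

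The count assumes daily dosing, no resupply between visits, and a visit-day dose from the old bottle, as the protocol says. If that dose came from the new bottle, gaps of 11, 12 and 13 days would miss 0, 1 and 2 doses.

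**What to change.** Add one sentence to Table 1 footnote a, 7.1.2.1 and 7.1.2.2: each visit stays within ±3 days of its day counted from Visit 0, and consecutive visits may be no more than 10 days apart. This is always feasible. After a visit 3 days early, the next can be as late as its nominal day, because −3 + 10 = 7. It also settles the two readings of the window in titration.

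The cost is a little scheduling freedom after an early visit. For example, after Visit 5 on day 32, Visit 6 on days 43 to 45 would become a deviation. No extra product goes home and no analysis changes. A second bottle whenever the booked gap exceeds 10 days would keep the full window, but it sends more of a controlled substance home. If the interactive response system already has a resupply rule, stating it in the protocol would serve equally well.

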### 7.1.2.3 End-of-Study Visit (Visit 6/Early Termination)

All randomized subjects who complete the study or discontinue early will complete Visit 6/early termination (ET).

[Table 1](#) lists the procedures to be completed at Visit 6/ET and should serve as the primary point of reference regarding visit-specific study procedures.

Further clarification on the procedures performed during Visit 6/ET is provided below:

- Unused investigational product and empty containers will be collected to calculate medication compliance.
- After 5 minutes rest, blood pressure and pulse will be collected 3 times (with at least 2 minutes in between each collection) during the visit. The average of each set of 3 measurements will be used to determine continued participation in the study (see [Section 4.4.1](#)).

### 7.1.3 Safety Follow-up Period

The follow-up period for this protocol is 7 days +3 days from the last dose of investigational product.

At the end of this period there will be a telephone call initiated by the site staff to query for serious adverse events (SAEs), AEs, and concomitant treatments. All AEs and SAEs that are not resolved at the time of this contact will be followed to closure (see [Section 8.1](#)).

### 7.1.4 Additional Care of Subjects After the Study

Subjects who have completed the study at Visit 6 end of study (EOS)/ET may be evaluated for eligibility to enter a long-term safety study of SPD489.

## 7.2 Study Evaluations and Procedures

The individual indicated in each scale description will perform all assessments listed below. Assessments are to be performed according to the schedule shown in [Table 1](#). Care must be taken by the site personnel or the investigator to fully explain the scale prior to completion.

If the subject terminates treatment early, all assessments listed in [Table 1](#) for Visit 6/ET and the Safety Follow-up Call should be completed. Whenever possible, raters (including parent(s)/LAR and the investigator or site designee) observing the subject's behavior should be consistent from visit to visit throughout the study.

